11.2. Methods for Evaluation of Disease

ROI's should be drawn around the solid nonfat portions of the tumor. One should evaluate signal intensity on arterial and portal venous phase images using identical delay times after start of injection for each time. For the exploratory objective 2.3.1, principles of Choi response criteria should be use (measure AUC for first 30 seconds post injection).

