2.3. Exploratory Objectives

- 1) To determine whether volumetric response rates in sporadic AMLs to everolimus qualitatively correspond to perfusion/angiogenic content/vascularity of baseline tumor as measured by qualitative DCE MRI using the principles of Choi response criteria (AUC for first 30 seconds post injection).
- 2) To investigate and explore potential molecular mechanism(s) of response and/or resistance of sporadic AMLs to everolimus treatment using a) initial diagnostic tumor tissue samples and if a biopsy or tumor resection is clinically indicated and pursued that tumor tissue sample and b) serum cfDNA.

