11.0 Measures of Effect

11.1. Response Evaluation Utilizing DCE-MRI

DCE-MRI assessments will be performed at baseline, on Cycle 5 Day 1, on Cycle 6 Day 28, and 12 months after the start of treatment. The Cycle 6 Day 28 MRI and the 12 month MRI will be done even if patient doesn't continue onto cycles 5 and 6.

Location and size of the IV, as well as type and amount of contrast and injection rate should be the same for all time points of each individual patient. These can be different between patients.

Protocol should contain at minimum breathhold axial T1W in and out of phase multiplanar gradient echo sequence. To evaluate volume of the index lesion perform axial and coronal breathhold T1W 3-d gradient echo sequences with and without fat saturation (VIBE, LAVA/FAME and THRIVE for Siemens, GE and Philips respectively). Then, dynamic pre and post contrast enhanced nonbreathhold coronal T1W fast 3-d gradient echo sequences to run for two minutes. Each individual volume acquisition time should be maximum 4-5 seconds. These should be lower resolution with 5 mm slice thickness and adjust slice number to cover the size of the index lesion usually 15-20 slices. Phase encoding of 128 or less to keep acquisition time of less than 5 seconds. Patients should be instructed to perform shallow breathing. Start injection of the contrast 15 seconds after the start of the acquisitions. Acquisitions stop at 2 minutes after the start and at 2.5 minutes repeat the coronal and axial breathhold T1W fast 3-d gradient echo sequences with fat sat in that order.

Choose a central slice of the index lesion on the pre and post coronal breathhold images and trace the perimeter and get a signal intensity number for both. If possible choose a slice with a large soft tissue component and trace that separately pre and post. Calculate a percent enhancement as follows: $(\text{Post} - \text{Pre}/\text{Pre}) \times 100$. Dynamic data can be used to choose post time point with maximum enhancement. If possible, calculate an AUC 45 (area under the curve for 45 seconds) from the dynamic data. Volumes can be calculated on the breathhold 3-d sequences with or without fat sat. If dynamic sequences are unusable secondary to artifacts, then percent enhancement can be calculated from the breathhold 3-d T1W sequences with or without fat sat.

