To ensure oversight with respect to toxicity, an interim review will be conducted if the early stopping rule for toxicity is reached in the first 18 patients. For this interim review, all available data related to primary and secondary efficacy and toxicity endpoints will be collected, summarized and presented. The data will be reviewed at a meeting of the invested trial parties, including but not limited to investigators at all participating sites (PIs or representatives at outside centers may call in to the meeting), staff on the research team, members of the FCCC Investigator Sponsored Research Unit, and statistics team. A summary recommendation will emerge from the meeting as to whether the study should be terminated or modified to a new dosing schema. This recommendation will be forwarded to the FCCC DSMB for signoff. Study accrual will halt until the outcome of the interim review is accepted by the FCCC DSMB. If the DSMB does not concur with the findings of the Investigator Meeting, the local FCCC IRB will review the trial for final decision.

In secondary analyses we will use graphs, standard descriptive statistics (mean, median, minimum, maximum, standard deviation, two-sided 95% confidence intervals) and Generalized Estimating Equation methods to characterize and model longitudinal health-related quality of life (HRQoL) measurements. Tumor regrowth kinetics will be characterized by the percent change in volume from the date of everolimus treatment termination. Values will be summarized using plots and standard descriptive statistics (mean, median, minimum, maximum, standard deviation, two-sided 95% confidence intervals) separately for each measurement following treatment discontinuation. Safety and tolerability objective will be measured by the incidence of adverse events, serious adverse events, deaths and laboratory abnormalities. Spearman's correlation coefficients will be computed to estimate the association between the largest percentage volumetric response from baseline with levels of perfusion/angiogenic content/vascularity of baseline tumor as measured by DCE MRI.

We will tabulate the frequencies of all grade 2 or higher adverse events as defined by NCI CTCAE version 4 criteria. The criteria are available online at <http://ctep.cancer.gov/reporting/ctc.html>.

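### The perfusion AUC window starts at injection with no correction for contrast arrival, so differences in transit time between patients add error to the baseline ranking behind the exploratory Spearman correlation (minor)

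*Combined protocol and SAP*

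**What the plan says.** Exploratory objective 1 in section 2.3 asks whether volume response corresponds to baseline tumour vascularity, using the "AUC for first 30 seconds post injection". Section 11.2 repeats the rule: "measure AUC for first 30 seconds post injection".

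Section 11.1 describes the dynamic run. "Start injection of the contrast 15 seconds after the start of the acquisitions"; "Each individual volume acquisition time should be maximum 4-5 seconds"; "Acquisitions stop at 2 minutes after the start". It also says: "If possible, calculate an AUC 45 (area under the curve for 45 seconds) from the dynamic data", without giving a start point for those 45 seconds. Cannula site and size and the "type and amount of contrast and injection rate should be the same for all time points of each individual patient", but the next sentence allows all of these to differ between patients.

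Section 12.1 plans Spearman correlations between the largest percentage volume response and the "levels of perfusion/angiogenic content/vascularity of baseline tumor as measured by DCE MRI".

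None of these sections mentions contrast arrival, onset of enhancement or an arterial reference.

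**The concern.** Contrast given into a vein reaches the kidney after a delay that varies between patients. When the clock starts at injection, the first part of the 30 seconds contains no enhancement, and how much of the enhancement curve falls inside the window depends on that delay. Two tumours with identical uptake therefore receive different AUC values if their arrival times differ.

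The within-patient standardisation in section 11.1 protects repeat scans of one patient. It does not help the analysis in section 12.1, which compares patients with each other at baseline. If transit time is unrelated to response, the added error attenuates the correlation, and a real link between vascularity and response could look weaker than it is. If transit time is related to response through some patient characteristic, part of that relation would be credited to vascularity.

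**Working it through.** The plan states no figure for the AUC, so there is none to reproduce.

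**Inputs from the documents.** The window is 0-30 s after injection (2.3, 11.2). Frames last 4-5 s, injection is at 15 s and the run ends at 120 s (11.1). The window therefore holds 30/5 = 6 to 30/4 = 7.5 frames, and 120 − 15 = 105 s of post-injection data are recorded.

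**Assumptions, not in the documents.** These are the arrival time ta, the shape of the enhancement curve and the spread of true uptake k between tumours.

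**Same uptake, different arrival.** Let d = 30 − ta.
- Step curve: AUC = k·d.
- Linear rise throughout the window: AUC = k·d²/2.

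| Arrival ta | d | Step (k = 1) | Linear (k = 1) |
|---|---|---|---|
| 15 s | 15 | 15 | 112.5 |
| 20 s | 10 | 10 | 50 |
| 25 s | 5 | 5 | 12.5 |

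- 15 versus 25 s: 15/5 = 3.0 (step) and 112.5/12.5 = 9.0 (linear). Exponential rises with time constants of 5-20 s lie between, at 5.6-7.7.
- 15 versus 20 s: 15/10 = 1.5 (step) and 112.5/50 = 2.25 (linear).
- Other assumed pairs widen the range, from 15/12 = 1.25 (15 versus 18 s, step) to (20/5)² = 16 (10 versus 25 s, linear).

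**Effect on ranking.** I simulated 43 patients per trial, with log-normal k, arrival uniform over the stated range and a linear rise lasting 20 s. The entries are the mean Spearman correlation of the written 30 s AUC with true k.

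| Log-SD of k | Arrival 15-25 s | Arrival 15-20 s |
|---|---|---|
| 0.3 | 0.41 | 0.75 |
| 0.5 | 0.59 | 0.88 |
| 0.8 | 0.76 | 0.95 |
| 1.0 | 0.82 | 0.96 |

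With a step curve, arrival 15-25 s and log-SD 0.3-0.5, the values are about 0.65-0.83. With a 30 s window that starts at arrival, located with a uniform error of ±2.25 s (half a 4.5 s frame), the linear-rise values are 0.97-0.99 throughout.

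**Dependence on window length.** Take 45 s from injection with the same curve, which rises for 20 s and is then flat. The AUC is 200 + 20 × 10 = 400 for arrival at 15 s, 300 at 20 s and 200 at 25 s, so the spread for 15 versus 25 s falls to 2-fold. The Spearman correlation at log-SD 0.3-0.5 rises to 0.80-0.91.

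**Feasibility of re-anchoring.** A 30 s window fits within the recorded data for any arrival up to 105 − 30 = 75 s after injection.

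**The case against.** A reader might infer that the AUC mostly measures transit time, or that equally vascular tumours are ranked up to 9-fold apart. The documents support neither. They give no transit time, curve shape or spread of vascularity. Nine-fold is one scenario (15 versus 25 s with a linear rise) within a range of about 1.3 to 16, so it is neither a bound nor a central value. With assumed mean arrival of 18 s, SD 2-4 s and a coefficient of variation of vascularity of 30-80%, transit accounts for anything from 6% to 88% of the variance of log AUC. Section 1.1 describes these tumours as mixed in composition, so a wide spread is plausible, although section 11.2 restricts the region of interest to nonfat tissue. With a wide spread the AUC mainly tracks vascularity.

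Four further points stand. The objective is exploratory and framed as qualitative. The Spearman sentence does not name the 30 s AUC, and section 11.1 also specifies percent enhancement, with the post-contrast time point allowed at maximum enhancement, which depends much less on arrival. The size of the problem depends on the unresolved choice between 30 and 45 s. Finally, section 11.1 sizes the dynamic slab only to cover the index lesion, so the aorta or renal artery may not be imaged.

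None of this removes the point. For any rising or sustained curve that arrives within the window, later arrival lowers the written AUC at equal vascularity, and no text corrects for it.

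**Conclusion.** The point holds as a minor one, confined to exploratory objective 1 in section 2.3. That the window is tied to injection, that injection set-up may differ between patients, and that the analysis compares patients all follow from the text. The size does not. It rests on assumed arrival times, curve shape and uptake spread, and within those assumptions the loss of ranking accuracy runs from slight (0.96) to substantial (about 0.4). The 0.97-0.99 for an arrival-based window is optimistic, because the simulation includes no image noise, breathing motion or differences in injection between patients. Attenuation towards zero further assumes that transit time is unrelated to response. The primary volume response, the sample size and the stopping rules are not affected.

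**What to change.** In sections 2.3 and 11.2, define the AUC over a fixed window that starts at the first frame showing contrast arrival on the same dynamic series, after subtracting the mean pre-contrast signal. Read arrival from the aorta or renal artery if either lies in the slab, and otherwise from first enhancement of the cortex of the same kidney.

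Use the same length and start point in section 11.1. As written, its 45 s AUC would end at 45 − 15 = 30 s after injection if counted from the start of acquisition, but at 45 s after injection if counted from injection, so the two definitions may or may not agree. Name the resulting value in section 12.1 as the perfusion measure for the Spearman analysis.

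The cost is a sentence in each of these sections and one extra region of interest per baseline scan. Arrival is located only to within one 4-5 s frame. No additional scan is needed.

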11.3. Response Criteria

Patients who have $\geq 25\%$ decrease in tumor volume after 4 cycles of everolimus therapy will continue study drug for 2 additional cycles. Those with $< 25\%$ reduction or a new lesion (defined at 1 cm in longest diameter or more) will be taken off treatment.

11.4. Health Related Quality of Life

Health-related quality of life will be assessed with the use of patient responses to the 19-item Functional Assessment of Cancer Therapy (FACT) Kidney Symptom Index (FKSI-19; on a scale from 0 to 76, with higher scores indicating fewer symptoms)¹⁸ (Appendix III). The instruments will be administered at baseline, on day 1 of each 28 day cycle, at study drug discontinuation and at the final study visit.

11.5. Serum Correlatives

PBMC, serum and plasma will be collected at baseline to look for evidence of mTOR inhibition – seeing an increase in pAKT and a decrease/inhibition of pS6—as well as future research like plasma RNA (nanostrip panel) and cfDNA. For cfDNA blood will be collected at a single time point using either two 7ml STRECK tubes per patient (if cannot be frozen immediately) or frozen as per the lab manual. cfDNA will be extracted using QIAamp circulating nucleic acid kit and stored for future use.

12.0 Statistical Considerations

12.1. Study Design/Endpoints

The required sample size for this trial is 43 patients, using a Simon two-stage design. The sample size justification and details are below.

We will conduct a single arm Phase II study to assess the efficacy of everolimus in patients with ≥ 3 cm sporadic AMLs. Response for a patient will be defined by a decrease in size of $\geq 25\%$ after 4 cycles of treatment.

We will implement an optimal two-stage Simon design for this trial. The new treatment would be of interest if the proportion, p , of responding patients is at least 25%. A proportion of patients with a response rate of less than 10% will be of no interest. Forty three (43) patients will allow us to test the null hypothesis: $p \leq 10\%$ against the alternative hypothesis: $p \geq 25\%$ at the 5% level of significance (α) with 80% power for a one-sided test. The early stopping point is 18 patients for both efficacy and toxicity. For efficacy, if 2 or fewer patients respond among the first 18 patients then the null hypothesis will not be rejected and the trial will be terminated. The probability of early stopping under the null is 73%. If the trial progresses until 43 patients are evaluated and 8 or more patients respond, then the null hypothesis will be rejected.

For toxicity, the trial will be paused and termination considered if out of the first 18 patients, 3 or more come off trial due to any adverse events as defined in the protocol. If the study proceeds to stage II (total enrollment = 43 patients), the trial will be paused and termination considered if at any point 8 or more patients come off trial due to any adverse events as defined in the protocol. If the true rate of any adverse events necessitating a patient to come off trial is 20%, the probability of early stopping is 73%; if the true rate of any adverse events necessitating a patient to come off trial is 5%, the probability of early stopping is 6%. Pause and

termination consideration for toxicity will occur, either early or finally, with probability 81% if true toxicity proportion is 20%; and 6% if it is 5%.

To ensure oversight with respect to toxicity, an interim review will be conducted if the early stopping rule for toxicity is reached in the first 18 patients. For this interim review, all available data related to primary and secondary efficacy and toxicity endpoints will be collected, summarized and presented. The data will be reviewed at a meeting of the invested trial parties, including but not limited to investigators at all participating sites (PIs or representatives at outside centers may call in to the meeting), staff on the research team, members of the FCCC Investigator Sponsored Research Unit, and statistics team. A summary recommendation will emerge from the meeting as to whether the study should be terminated or modified to a new dosing schema. This recommendation will be forwarded to the FCCC DSMB for signoff. Study accrual will halt until the outcome of the interim review is accepted by the FCCC DSMB. If the DSMB does not concur with the findings of the Investigator Meeting, the local FCCC IRB will review the trial for final decision.

In secondary analyses we will use graphs, standard descriptive statistics (mean, median, minimum, maximum, standard deviation, two-sided 95% confidence intervals) and Generalized Estimating Equation methods to characterize and model longitudinal health-related quality of life (HRQoL) measurements. Tumor regrowth kinetics will be characterized by the percent change in volume from the date of everolimus treatment termination. Values will be summarized using plots and standard descriptive statistics (mean, median, minimum, maximum, standard deviation, two-sided 95% confidence intervals) separately for each measurement following treatment discontinuation. Safety and tolerability objective will be measured by the incidence of adverse events, serious adverse events, deaths and laboratory abnormalities. Spearman's correlation coefficients will be computed to estimate the association between the largest percentage volumetric response from baseline with levels of perfusion/angiogenic content/vascularity of baseline tumor as measured by DCE MRI.

We will tabulate the frequencies of all grade 2 or higher adverse events as defined by NCI CTCAE version 4 criteria. The criteria are available online at <http://ctep.cancer.gov/reporting/ctc.html>.

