3.0 Study Plan

After confirming eligibility criteria, patients will be enrolled in this study. Volumetric and perfusion/vascularity analyses will be done by DCE-MRI at baseline. Patients will then receive everolimus 10 mg daily. Treatment duration will be continuous for 4 cycles unless treatment is discontinued.

After 4 cycles of treatment, repeat imaging with DCE-MRI will be performed to assess tumor size kinetics (sum of volumes of all target AMLs identified at baseline). If the tumor has decreased in size by greater than or equal to 25% and no new AMLs greater than 1 cm in longest diameter have appeared, then the drug will be continued for another two cycles (6 cycles total treatment). If on the other hand the tumor has grown or decreased by less than 25% or there are new AMLs (at least 1 cm in longest diameter), then the drug will be discontinued.

At the end of cycle 6 and 12 months after start of therapy with everolimus, imaging via DCE MRI will be repeated to assess growth/regrowth kinetics/qualitative perfusion.

If for any reason a patient terminates treatment with everolimus earlier than the end of cycle 4, all imaging will still be performed and used for the statistical analysis and primary endpoint calculations. Given that therapy with everolimus has potential toxicity and that the disease in question (sporadic AML) is not a malignant condition, patients will not be replaced if they drop out, in a way signaling that the therapy may not be feasible. If a patient receives at least one dose of everolimus they will be included in the analysis. If a patient does not get imaged after 4 cycles of treatment, for the purposes of statistical considerations they will be considered a non-responder.

Treatment related toxicities and QOL will be assessed at baseline, day 1 of each 28 day cycle, at drug discontinuation and at the last study visit

Tissue for exploratory objectives will be collected at baseline only if available from archival tissue. Additional tissue will also be collected if the patient undergoes a partial or complete nephrectomy or embolization during the study period for the AML. Serum at baseline will also be collected for cfDNA and other future potential correlative studies.

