5.4. **Criteria for Discontinuation**

Patients will be removed from treatment if one of the following criteria applies:

- Disease progression including:
 - Bleeding or pain
 - Requirement for surgical or percutaneous intervention
 - Greater than a 25% increase in tumor volume of AML
- Intercurrent illness that prevents further administration of treatment

- Unacceptable adverse events
- Treatment is temporarily held for > 21 days
- Patient becomes pregnant
- Patient decides to withdraw from the study
- General or specific changes in the patient's condition that render the patient unacceptable for further treatment in the judgment of the investigator.

The reason for discontinuation and the date the patient was removed must be documented in the medical record and case report form.

5.5. **Optional Tissue and Blood Collection for Exploratory Objectives**

At time of trial initiation, patients will be consented to allow the use of their tissue and blood for future research, specifically including, but not limited to, the analysis of mTOR alterations, VEGF pathways and tumor genome sequencing (e.g. mutations (AKT/PI3K, PTEN), amplifications, deletions in TSC1 and TSC2).

At screening, if archival biopsy tissue of the AML is available, unstained slides will be requested. If a patient undergoes a clinical procedure where tissue will be obtained during the study, that tissue will also be collected for exploratory objectives. Biopsy, resection, and/or percutaneous intervention will be performed entirely at the discretion of the treating clinician based on individual clinical scenarios and needs.

An EDTA and red top tube will be collected to provide plasma, serum and peripheral blood mononuclear cells (PBMCs). All biological samples will be stored at Fox Chase Cancer Center for possible future research.

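### Section 12.1 counts a patient with at least 25% shrinkage and a new AML at the Cycle 5 Day 1 MRI as a responder, which does not fit sections 3.0, 5.0, 5.1 and 11.3

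*Combined protocol and SAP*

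**What the plan says.** - **12.1, primary endpoint:** "Response for a patient will be defined by a decrease in size of" 25% or more after 4 cycles. It sets no condition on new lesions.
- **3.0, what is measured:** the summed volume of the target AMLs identified at baseline.
- **3.0, what follows the scan:** the drug continues only with a decrease of at least 25% and no new AML above 1 cm. Growth, a smaller decrease, or a new AML of at least 1 cm stops it.
- **5.1:** the two further cycles require both the 25% reduction and no new AMLs.
- **11.3, headed Response Criteria:** a decrease of 25% or more leads to two more cycles. Patients with less than that "or a new lesion (defined at 1 cm in longest diameter or more) will be taken off treatment".
- **5.0:** partial response is a reduction of 25% or more, with no new-lesion condition, and patients with a partial response continue.
- **3.0, early stoppers:** the rule, whatever the reason for stopping, reads: "terminates treatment with everolimus earlier than the end of cycle 4, all imaging will still be performed and used for the statistical analysis". The same sentence applies this to the primary endpoint. The only patient whom 3.0 makes a non-responder by rule is one not imaged after 4 cycles.
- **5.4, a list of reasons to stop treatment:** under "Disease progression including" it names bleeding or pain, need for intervention, and growth of more than 25%.

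**The concern.** Take a hypothetical patient whose target sum is down 30% at the Cycle 5 Day 1 MRI, and whose same scan shows a new 2 cm AML. Under 12.1 this is a success. Under 3.0, 5.1 and the second sentence of 11.3 the patient is handled exactly like one whose tumor did not shrink enough. Two analysts could score this patient differently, each with a section to cite, and might have to choose after seeing the data.

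The trial has one arm and is decided by a small count, so there is no control group to absorb a lenient numerator. If the authors meant a new lesion to exclude response, 12.1 as written would overstate the rate they intended to test.

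**Working it through.** **1. The passages side by side, for a patient with at least 25% shrinkage and a new AML of at least 1 cm**

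| Section | Treatment of this patient |
|---|---|
| 12.1 | Responder |
| 5.0 | Partial responder, so continues |
| 5.1 | Does not qualify for further cycles |
| 3.0 | Drug stopped |
| 11.3 | First sentence: continues. Second sentence: off treatment |

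If every partial responder continues (5.0) and every patient with a new AML stops (3.0, 11.3), then a patient with a new AML cannot be a partial responder. Yet 5.0 and 12.1 define response by shrinkage alone. The sections agree only if a new AML excludes response, and none of them says so.

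**2. The plan's own design**

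Inputs, all from 12.1: "We will implement an optimal two-stage Simon design for this trial"; 43 patients; null rate 10%; alternative 25%; stop if 2 or fewer of the first 18 respond; reject the null if 8 or more of 43 respond.

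P(early stop) = Σ over x = 0 to 2 of C(18,x) p^x (1−p)^(18−x). At p = 0.10 this is 0.1501 + 0.3002 + 0.2835 = 0.7338. The plan says 73%.

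P(reject) = Σ over x = 3 to 18 of C(18,x) p^x (1−p)^(18−x) × P(Bin(25,p) ≥ 8−x). This gives 0.0480 at p = 0.10 and 0.8003 at p = 0.25. The plan says 5% and 80%.

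A search for the design with the smallest expected sample size under the null, at these rates and error limits, returns the same limits. There is no arithmetic error.

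**3. What the definition can change**

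At the limits, one patient decides: 3 of 18 continues and 2 of 18 stops; 8 of 43 rejects and 7 of 43 does not.

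Away from the limits, the effect depends on f, the share of volume responders who also have a new AML. The documents give no value. **The range 0 to 20% is an assumption.** Call response without a new AML the strict endpoint.

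| f | Volume rate if strict rate is 10%: 0.10/(1−f) | P(reject) under 12.1 as written | Strict rate if volume rate is 25%: 0.25(1−f) | P(reject) on strict endpoint |
|---|---|---|---|---|
| 0 | 10.0% | 0.048 | 25.0% | 0.800 |
| 5% | 10.5% | 0.061 | 23.75% | 0.753 |
| 10% | 11.1% | 0.079 | 22.5% | 0.697 |
| 15% | 11.8% | 0.101 | 21.25% | 0.634 |
| 20% | 12.5% | 0.131 | 20.0% | 0.564 |

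The third column is the chance of a positive trial when the strict rate is only 10%. The last column is the power left if 25% was set for volume alone and the strict endpoint is tested. In patients, f = 10% at a volume rate of 25% is 43 × 0.25 × 0.10 = 1.1 of 43.

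**The case against.** The strongest reply is that nothing is wrong. The primary objective in 2.1 is to reduce tumor volume. Section 5.0 defines partial response by shrinkage alone, and 12.1 matches it. The new-AML wording in 3.0, 5.1 and 11.3 governs whether the drug continues, and a stopping rule may legitimately differ from an endpoint. For the volume hypothesis that 12.1 states, the error rate stays at 4.8%. The overlap is also likely to be small: section 1.1 ties bilateral multifocal AMLs to tuberous sclerosis, which 4.2.1 excludes.

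Much of this stands. A volume-only endpoint is defensible, there is no error inflation for the hypothesis as written, and the effect is probably small. What does not stand is that the text is settled. Section 11.3 places the new-lesion condition under a response heading, and 5.0 sends all partial responders on to further treatment, which 3.0 and 5.1 forbid for this patient.

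A reader might go further and infer that 12.1 is also wrong to count a patient who stopped the drug for an AML bleed, or for other progression under 5.4, and whose scan still shows 25% shrinkage. The documents do not support that. Section 3.0 deliberately uses the imaging of patients who stop early for any reason. Section 5.4 is a list of reasons to stop treatment, and its bleeding or pain item carries no grade, attribution or comparison with baseline. Building it into the endpoint would put an unblinded judgment into an MRI measurement. It would also depend on whether the patient was still on drug: one already off drug for toxicity who then bleeds may have no 5.4 entry. Nor are such events hidden, since intervention at 1 year is a secondary objective and adverse events are tabulated.

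**Conclusion.** The point holds for new AMLs. As written, shrinkage of at least 25% together with a new AML of at least 1 cm on the Cycle 5 Day 1 MRI is a response in the Simon test, and 3.0, 5.0, 5.1 and 11.3 cannot all be reconciled with that.

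The practical effect is probably small, except at 3 of 18 or 8 of 43, where one patient reverses the decision. The figures in the table rest wholly on the assumed overlap and show direction and scale only. A reader might take 0.061 to 0.131 as the trial's true type I error. It is not: those values apply only if the 10% null is meant for the strict endpoint and 5 to 20% of volume responders have a new AML.

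Handling 5.4 progression as non-response in the primary endpoint is a design preference, and its absence is not a defect.

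**What to change.** In 12.1, define response on these lines: at the Cycle 5 Day 1 MRI, the summed volume of the baseline target AMLs is at least 25% below baseline, and no new AML as defined in 11.3 (1 cm or more) is present. Report the volume-only rate as a supportive result.

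Align the partial-response wording in 5.0 with this definition, and reconcile it with 3.0, 5.1 and 11.3. This concerns scoring only. Which patients continue treatment is for the sponsor to settle.

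Keep the 3.0 rules that imaging of early stoppers is used and that patients not imaged after 4 cycles are non-responders. Report bleeding, pain or other 5.4 progression before the scan alongside the response rate, or add a sensitivity analysis that counts those patients as non-responders.

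**Cost:** a sentence in 12.1 and a small edit to 5.0. The MRI is already scheduled. The sample size of 43 and both limits stay if 10% and 25% are meant for this endpoint, and 12.1 should say so. The response rate may come out slightly lower. If 25% was set for volume alone, power falls as in the last column of the table, for example to 0.697 at an assumed 10% overlap. If the sponsor does intend volume alone, 12.1 should state that a new AML does not exclude response, and 5.0 and 11.3 should be worded to match.
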